10.9 Reporting Serious Adverse Events and Adverse Events of Special Interest

The Investigator must report all Serious Adverse Events (SAEs) and all Adverse Events of Special Interest (AESIs) to the [REDACTED] Safety Contact listed below within 24 hours of awareness. The information must be sent by providing the completed SAE/AESI form. The [REDACTED] Safety Contact will report all information to Chiesi Global Pharmacovigilance, the Clinical Project Manager and the Clinical Research Physician.

Name and Title	E-mail
[REDACTED] Safety Contact	[REDACTED]
Chiesi Safety Contact	[REDACTED]

- The reporting period for SAEs from the investigator site is from the time of subject's signature of informed consent and until the subject's study participation ends. After this date, even if no active monitoring of subjects is required, SAEs occurring to a subject should be reported if the investigator becomes aware of them.
- Reporting of AESI is from the time the subject is administered the first dose of study drug on Day 1 until the 30 days \pm 2 days follow up assessment.
- Up to the closure of the site, SAE reports should be reported to the [REDACTED] Safety Contact. New serious adverse events occurring after the site is closed should be reported directly to the Chiesi Safety Contact.
- The SAE and AESI information should also be completed simultaneously in the adverse event page of the case report form (CRF).

10.10 Reporting Serious Adverse Events to Regulatory Authorities/Ethics Committees/IRB

Chiesi or [REDACTED] will report serious unexpected adverse reactions to the regulatory authorities in compliance with the timelines and standards of reporting according to local regulations as well as to the Investigators, ethics committees and Central IRB, if applicable, by MedWatch/CIOMS form. The Investigator is responsible for local IRB reporting per Sponsor

 Chiesi	Clinical Study Protocol
Clinical Study Code No.: CUSA-081-HEM-01	Version No.: 8.0
EUDRACT No./IND No.: 2019-002124-32/128551	Date: 21 FEB 2023

instruction upon receipt of the SUSAR notification. Participating Investigators, ECs and IRBs will receive a blinded IND Safety Report, unless otherwise specified.

All SUSARs, which occur with the investigational medicinal products within or outside the concerned clinical trial, if required, will be reported in compliance with the timelines and standards for reporting SUSARs as set out in FDA 21 CFR part 312.32 and the EU Directive 2001/20/EC [Directive 2001/20/EC of the European parliament and of the council of 4/April/2001] and linked guidance [European Commission, Enterprise and Industry Directorate General: Detailed guidance on the collection, verification and presentation of adverse event/reaction reports arising from clinical trials on medicinal products for human use, latest version]. The EMA and the concerned national health authority (if applicable) will be informed through Eudravigilance, while the Ethics Committees and the investigators by CIOMS I form or by periodic line- listings produced by Chiesi Global Pharmacovigilance. The EMA and the concerned national health authority (if applicable) will be informed through Eudravigilance, while the Ethics Committees and the investigators by CIOMS I form or by periodic line- listings produced by Chiesi Global Pharmacovigilance.

With regard to regulations in force for Pharmacovigilance, the Investigator must fulfill his/her obligation according to the law in force in his/her country.

10.11 General Notes

- In case of death, a comprehensive narrative report of the case should be prepared by the Investigator and sent to the CRO Safety Contact by fax together with the Serious Adverse Event form, retaining a copy on site.
- If an autopsy is performed, copy of autopsy report should be actively sought by the Investigator and sent to the CRO Safety Contact as soon as available, retaining a copy on site.
- In case of pregnancy, the subject will be followed with due diligence until the outcome of the pregnancy is known and until the age of one year to detect any congenital anomaly or birth defect. The pregnancy must be reported by the investigator within 24 hours by fax/e-mail/via Monitor to the [REDACTED] Safety Contact using the paper Pregnancy Report Form. [REDACTED] Safety Contact will inform Chiesi of the pregnancy within one working day of being notified.

The first two pages of the Pregnancy Report Form should be completed by the investigator with all the available information and sent to the CRO Safety Contact. The third page will be completed as soon as the investigator has knowledge of the pregnancy outcome, together with a follow-up of the first two pages, if necessary (e.g. an update in the medications received during pregnancy by the mother). If it meets the criteria for immediate classification of a SAE (e.g. spontaneous or therapeutic abortion, stillbirth, neonatal death, congenital anomaly, birth defect) the Investigator should follow the procedure for reporting SAEs.

- If it is the partner, rather than the subject, who is found to be pregnant, the same procedure regarding pregnancy reporting is to be followed and the Pregnancy Report Form should be completed.

 Chiesi	Clinical Study Protocol
Clinical Study Code No.: CUSA-081-HEM-01	Version No.: 8.0
EUDRACT No./IND No.: 2019-002124-32/128551	Date: 21 FEB 2023

- If the pregnancy is discovered before taking any dose either of study drug medication, the subject will not be eligible for the study and the pregnancy does not need to be reported.
- Any ADR occurring with any marketed non-IMP and/or concomitant medication during the study must be reported by the Investigator to his/her concerned Health Authority according to the applicable laws. The Investigator is also recommended to report all ADRs to the relevant Marketing Authorisation Holders of the involved medicinal products. Additionally, conditions of use outside the marketing authorisation of the medicinal products (i.e. off label, overdose, misuse, abuse and medication errors) or from occupational exposure, as well as cases of suspected treatment interaction, pregnancy, breastfeeding exposure and lack of efficacy should be reported

11. DATA MANAGEMENT

An electronic CRF (eCRF) will be completed by the Investigator and/or his/her designee for all subjects including screen failures.

Front-end edit checks will run at the time of data collection and back-end edit checks will be used by the Data Manager to check for discrepancies and to ensure consistency and completeness of the data.

Medical history and Adverse Events will be coded using the MedDRA dictionary; medications will be coded using the WHO Drug dictionary and Anatomical Therapeutic Chemical classification (ATC).

Access to electronic systems used for data collection will be granted to the study personnel only after appropriate training.

After cleaning of the data, review meetings will be held to determine the occurrence of any protocol violations and to define the patient populations for the analysis. This process will occur for the first set of patients which will be involved in the interim analysis, and then for all subsequent patients that will be randomized up to study recruitment closure. Only completed and discontinued patients at the time of the cut-off will be included in the interim analysis.

Once all data of patients included in the interim futility analysis have been declared to be complete and accurate, the database will be locked (“interim database lock”), the randomization codes will be opened (only for the patients involved in the interim analysis) and shared only with the Unblinded Statistical/Programming Team and the independent DMC responsible for the conduction or interpretation of the interim analysis. Additional details on the interim analysis and involved parties are provided in [Section 12.3.7](#).

A final database lock will occur once all data related to the patients enrolled in the study have been declared complete and accurate; the randomization list will be shared to the Sponsor and the final statistical analysis as planned in the SAP will be performed.

If the database is unlocked after the initial lock, the process must be carefully controlled and documented; updates to the study data must be authorized by Chiesi. This applies to the interim database lock for patients included in the interim futility analysis as well as for the final database lock including all patients.

At the study conclusion, a complete copy of the study data will be created for archival purposes at Chiesi. The investigators will receive copies of the patient data for retention at the investigational sites.

 Chiesi	Clinical Study Protocol
Clinical Study Code No.: CUSA-081-HEM-01	Version No.: 8.0
EUDRACT No./IND No.: 2019-002124-32/128551	Date: 21 FEB 2023

12. STATISTICAL METHODS

12.1 Sample Size

Hypotheses

The primary objective is to demonstrate superiority of CUSA-081 compared to placebo in the rate of treatment success (restoration of CVAD function) following a single administration with a dwell time up to 90 minutes. The primary hypotheses are as follows:

The null hypothesis H0: $R_c - R_p = 0$

The alternative hypothesis H1: $R_c - R_p > 0$

R_c =Rate of success of CUSA-081

R_p =Rate of success of placebo

The first secondary objective is to demonstrate non-inferiority of CUSA-081 vs alteplase in the rate of treatment success following a single administration with a dwell time up to 90 minutes. The hypotheses for the non-inferiority are as follows:

The null hypothesis H0: $R_c - R_a \leq -10$

The alternative hypothesis H1: $R_c - R_a > -10$

R_c =Rate of success of CUSA-081

R_a =Rate of success of alteplase

Additional hypotheses are constructed in a similar manner for secondary objectives to demonstrate superiority of CUSA-081 vs alteplase following a single administration with a dwell time up to 90 minutes, and to demonstrate superiority of CUSA-081 compared with placebo in the rate of treatment success at different time points, after one or two administrations. The order of the remaining secondary objectives is listed below:

2. Superiority of CUSA-081 compared to placebo in the rate of treatment success after a single administration with a dwell time up to 60 minutes;
3. Superiority of CUSA-081 compared to placebo in the rate of treatment success after up to two administrations with a dwell time up to 180 minutes;
4. Superiority of CUSA-081 compared to alteplase in the rate of treatment success after a single administration with a dwell time up to 90 minutes.

Significance Level

The comparisons of superiority will be performed at the two-sided 5% level of significance. The assessment of non-inferiority will be based on the 2.5% level of significance (using one-sided 97.5% confidence intervals) with a non-inferiority margin of -10%.

Multiplicity Adjustment

[figure not shown]
Multiplicity adjustment for testing of multiple hypotheses. A closed testing procedure will be used to control the overall type I error rate at <5%. The hypothesis testing will start with the primary objective, then the secondary efficacy objectives will be tested, in the order listed in

Chiesi	Clinical Study Protocol
Clinical Study Code No.: CUSA-081-HEM-01	Version No.: 8.0
EUDRACT No./IND No.: 2019-002124-32/128551	Date: 21 FEB 2023

the study objectives and shown in the figure below, until a null hypothesis is not rejected (a two-sided p-value >0.05 is observed, or lower limit of the two-sided 95% CI $\leq -10\%$ for the non-inferiority assessment).

Figure 2: Statistical Testing of Rate of Treatment Success in the READY-1 Trial

Treatment success is defined as restoration of CVAD functionality measured as the ability to withdraw 3 mL of blood and infuse 5 mL of saline.

Notes:

1. All tests are performed at the 2-sided $\alpha=0.05$ level of significance.
2. For tests at 60 and 90 minutes, the rate of treatment success is assessed as the percentage of subjects achieving treatment success following a single instillation of study drug and a dwell time up to 60 or 90 minutes, respectively.
3. For the test at 180 minutes, the rate of treatment success is assessed as the percentage of subjects achieving treatment success following up to two instillations of study drug and a dwell time up to 180 minutes, respectively.

Multiplicity adjustment not planned for interim analysis futility analysis. No multiplicity adjustment will be incorporated for the futility analysis to assess the conditional power for the non-inferiority test of CUSA-081 compared to alteplase in the rate of treatment success following a single administration of study drug with a dwell time up to 90 minutes (the second step in the closed testing procedure). Of note, there will be no stopping of any arm for efficacy and no claims of efficacy made on the basis of the futility analysis. The recommendation of a threshold to stop the study for futility will be considered as “nonbinding,” meaning the futility stopping criteria are guidelines to the DMC that may or may not be followed, depending on the totality of the available interim results.

 Chiesi	Clinical Study Protocol
Clinical Study Code No.: CUSA-081-HEM-01	Version No.: 8.0
EUDRACT No./IND No.: 2019-002124-32/128551	Date: 21 FEB 2023

Required Sample Size

For the primary assessment of the superiority of CUSA-081 vs. placebo, a sample size of 450 in the active arm (CUSA-081), and 50 in the control arm (placebo), will provide >99% power to detect a difference of $\geq 35\%$ using a two-sided test at significance level of 0.05. The expected placebo response rate is approximately 20%.

For the assessment of the non-inferiority of CUSA-081 vs alteplase, a sample size of 450 in the active arm (CUSA-081), and 300 in the control arm (alteplase) will provide 87% power at the 2.5% significance level (that is by using one-sided 97.5% confidence intervals) with a non-inferiority margin of -10%, assuming an equal response rate of 75% in the control arm (alteplase), and the active (CUSA-081) arm. A sample size of 450 in the active arm (CUSA-081), and 300 in the control arm (alteplase) will also provide 92% power to detect a difference of 10% between the success rates using a two-sided test at significance level of 0.05.

A minimum of 841 subjects will be randomized in order to achieve a minimum of 800 subjects completing the study.

Statistical Consideration of Non-Inferiority Margin

The selection of the non-inferiority margin was based upon the following reasoning. The non-inferiority margin must be less than the smallest treatment difference between standard therapy and placebo (M1), and at least part of the treatment effect of the standard therapy must be preserved for the test drug (M2).

The NI margin of -10% between reteplase vs. alteplase was selected based on the following statistical consideration:

M1 = the smallest treatment effect of alteplase over placebo

M2 = a fraction 50% of M1 is the most commonly used value

Table 8: Historical Placebo Response

Study / Time point	Number of responders / Sample size	% Response	Lower 95% CI	Upper 95% CI
TROPICS 1 (Gabrail et al, 2010)	120 minutes	11/47	23%	11% 36%
COOL 1 (Cathflo PI, 2017)	120 minutes	12/74	16%	8% 25%

Placebo responses have been reported in hemodialysis setting and in the central venous catheter setting. We included the available placebo responses data from 2 studies in the central venous access setting ([Table 8](#)) with a definition of treatment success similar to the one used in this study and with a timepoint assessment of ≥ 90 minutes. Based on the data from these two studies, we estimated the placebo response using a weighted analysis based on

 Chiesi	Clinical Study Protocol
Clinical Study Code No.: CUSA-081-HEM-01	Version No.: 8.0
EUDRACT No./IND No.: 2019-002124-32/128551	Date: 21 FEB 2023

a random effect model (DerSimonian-Laird). The weighted placebo response is 19% with 95% CI of 12.9% to 26.8%.

Based on the CATHFLO ACTIVASE product label, the restoration of catheter function was assessed at 30 and 120 minutes after the first instillation of alteplase (rtPA). The response at 90 minutes was estimated based on linear interpolation. [Table 9](#) shows the observed response rates at 30 minutes and 120 minutes and the estimated 95% CI at 90 minutes.

Table 9: Historical rtPA Response

Time point (COOL 2)	# of responders / Sample size	% Response	Lower 95%CI	Upper 95%CI
30 minutes	observed	516/995	51.9%	48.8%
90 minutes	linear interpolation	670/995	67.3%	64.4%
120 minutes	observed	747/995	75.1%	72.4%

Based on the linear interpolation, the lower bound of the 95% CI of rtPA response at 90 minutes is 64.4%. The upper bound of the 95% CI for the weighted placebo response is estimated to be 26.8%. Therefore, the rtPA margin over placebo is at least 37.6% at 90 minutes. To preserve 50% of M1 in a NI trial, a NI margin of 18.8% (half of 37.6%) would be reasonable.

A more conservative -10% NI margin between reteplase and alteplase will be used for the 90 minutes endpoint in this trial, which should preserve >70% of M1.

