Treatment duration	
Treatment configurations are summarized below:
 
  
 Treatment Arm	Syringe 1 (given at min 0)	Syringe 2 (given, if needed, at min 90)	
   
 A	CUSA-081	CUSA-081	
 
 B	placebo	placebo	
 
 C	alteplase	alteplase	
  
	Treatment Arm	Syringe 1 (given at min 0)	Syringe 2 (given, if needed, at min 90)	A	CUSA-081	CUSA-081	B	placebo	placebo	C	alteplase	alteplase
Treatment Arm	Syringe 1 (given at min 0)	Syringe 2 (given, if needed, at min 90)											
A	CUSA-081	CUSA-081											
B	placebo	placebo											
C	alteplase	alteplase											

Test product dose/route/regimen	Treatment Arm A: One or two doses of CUSA-081 (reteplase), 0.70 mg (0.4 unit) / 2 mL, will be administered directly into the catheter lumen
Reference product dose/route/regimen	Treatment Arm B: One or two doses of placebo (normal saline) will be administered directly into the catheter lumen Treatment Arm C: One or two doses of alteplase, 2 mg in 2 mL, will be administered directly into the catheter lumen
Number of subjects	A minimum of 841 randomized subjects: Treatment Arm A (CUSA-081), 473 subjects Treatment Arm B (placebo), 53 subjects Treatment Arm C (alteplase), 315 subjects Subjects will be randomized in a 9:1:6 ratio of CUSA-081: placebo: alteplase.
Study population	Subjects who are 18 years of age or older who have dysfunctional CVADs

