Sample size calculation	
For the primary assessment of the superiority of CUSA-081 vs. placebo, a sample size of 450 in the active arm (CUSA-081), and 50 in the control arm (placebo), will provide >99% power to detect a difference of $\geq 35\%$ using a two-sided test at significance level of 0.05. The expected placebo response rate is approximately 20%.
 
For the assessment of the non-inferiority of CUSA-081 vs. alteplase, a sample size of 450 in the active arm (CUSA-081), and 300 in the control arm (alteplase) will provide 87% power at the 2.5% significance level (that is by using one-sided 97.5% confidence intervals with a non-inferiority margin of -10%), assuming an equal response rate of 75% in the control arm (alteplase) and in the active (CUSA-081) arm. A sample size of 450 in the active (CUSA-081) arm and 300 in the control arm (alteplase) will also provide 92% power to detect a difference of 10 % between the success rates using a two-sided test at significance level of 0.05.
 
A minimum of 841 subjects will be randomized to achieve a minimum of 800 subjects completing the study.

Statistical methods	
Analysis Population:
 
 • Full analysis set (FAS): All randomized subjects who receive at least one dose of study drug and with at least one available evaluation of efficacy after the baseline. Analyses using the FAS will be based on the treatment randomized. The FAS will be the primary analysis set for all efficacy analyses. • Safety set (SS): All randomized subjects who receive at least one dose of study drug. Subjects discontinued after dosing will be part of the SS. Analyses using the SS will be based on the actual treatment received. The SS will be the primary analysis set for all safety analyses. • Intent-To-Treat analysis set (ITT): All randomized subjects regardless if they received treatment with study drug. The ITT will be based on the randomized treatment allocation. The ITT will be used for sensitivity analysis for the primary efficacy analyses. • Per-protocol analysis set (PPS): all subjects from the ITT population without any major protocol deviation (i.e., wrong inclusions, incomplete dosing, non-permitted concomitant

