## 5 Sample Size

For the primary assessment of the superiority of CUSA-081 vs. placebo, a sample size of 450 in the active arm (CUSA-081), and 50 in the control arm (placebo), will provide >99% power to detect a difference of  $\geq 35\%$  using a two-sided test at significance level of 0.05. The expected placebo response rate is approximately 20%.

For the assessment of the non-inferiority of CUSA-081 vs alteplase, a sample size of 450 in the active arm (CUSA-081), and 300 in the control arm (alteplase) will provide 87% power at the 2.5% significance level (that is by using one-sided 97.5% confidence intervals (CI)) with a non-inferiority margin of -10%, assuming an equal response rate of 75% in the control arm (alteplase), and the active (CUSA-081) arm. A sample size of 450 in the active arm (CUSA-081), and 300 in the control arm (alteplase) will also provide 92% power to detect a difference of 10% between the success rates using a two-sided test at significance level of 0.05.

A minimum of 841 subjects will be randomized in order to achieve a minimum of 800 subjects completing the study.

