### Non-Inferiority Hypotheses

The hypotheses for the non-inferiority are as follows:

The null hypothesis H0:  $R_c - R_a \leq -10$   
The alternative hypothesis H1:  $R_c - R_a > -10$

Where Rc=Rate of success of CUSA-081  
Ra=Rate of success of alteplase

Assessment of non-inferiority will be based on the 95% confidence interval for the difference in the rate of treatment success between CUSA-081 vs alteplase following a single administration with a dwell time up to 90 minutes.

Non-inferiority will be demonstrated (or null hypothesis will be rejected) when the lower limit of the 95% confidence interval for the difference in rate of success is greater than -10% (See Section 14.1).

The number and percent of subjects with treatment success by treatment group and time point will be summarized. The rate difference and associated 95% Wald confidence intervals between CUSA-081 and placebo or alteplase will be estimated. The between treatment comparisons will be performed using a 2-sample z test for proportions.

For superiority hypotheses, the primary analysis will be the analysis performed on the FAS. Analyses will be repeated based on the ITT and PP Sets as sensitivity analyses. For non-inferiority hypotheses, the analysis based on the PP Set will be considered as the primary analysis.

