## 12 Changes in the Planned Analyses from Study Protocol

- The protocol Section 12.2 describes the FAS as “the primary analysis set for all efficacy analyses”. The first secondary objective is “to demonstrate the non-inferiority of CUSA-081 compared to alteplase in the rate of treatment success following a single administration with a dwell time up to 90 minutes”. The primary analysis corresponding to this objective, which is included within the hierarchical closed testing procedure, will be based on the Per-Protocol Set, since this approach is considered as more conservative as per Section 5.2.3 of ICH E9. The FAS will be the primary analysis set for all efficacy analyses involving assessment of superiority.
- The protocol Section 12.3.7 describes an interim futility analysis. Since the study has been terminated by the Sponsor prematurely for other reasons, the futility analysis will not be conducted. The analysis to be conducted following the premature closure of the study will be exactly the analysis which is planned for end of study. The database lock and unblinding will be conducted according to the relevant SOPs of the Sponsor and CRO and the analysis conducted will be considered as the final study analysis.
- The definition of the Per-Protocol Set has been modified to use Safety Set instead of ITT Set in order to include in the Per-Protocol Set only treated subjects.

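### The 87% non-inferiority power assumes 75% success at 90 minutes, but the plan's own 90-minute alteplase estimate is 67.3%, which gives about 82%

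*Protocol*

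**What the plan says.** The first secondary objective is non-inferiority to alteplase in treatment success after one administration with up to 90 minutes' dwell. Protocol 12.1 (Required Sample Size) says 450 and 300 subjects give 87% power at the one-sided 2.5% level with a -10 point margin, "assuming an equal response rate of 75% in the control arm (alteplase), and the active (CUSA-081) arm". The Protocol Outline uses nearly the same words, "assuming an equal response rate of 75% in the control arm (alteplase) and in the active (CUSA-081) arm", and SAP 5 repeats that this sample "will provide 87% power at the 2.5% significance level". None of the three places gives a source or a time point for the 75%. All three also claim 92% power to detect a 10-point difference.

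The margin justification that follows (Protocol 12.1 and Table 9; SAP 5.1 and Table 3) takes historical alteplase rates of 516/995 (51.9%) at 30 minutes and 747/995 (75.1%) at 120 minutes. Of the time in between it says: "The response at 90 minutes was estimated based on linear interpolation". The result is 670/995, or 67.3%, with a 95% CI of 64.4% to 70.3%.

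SAP 9.1 adds: "For non-inferiority hypotheses, the analysis based on the PP Set will be considered as the primary analysis". SAP 12 records this as a change from the protocol. Neither document gives power for that set.

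**The concern.** The plan holds two different alteplase success rates for the same 90-minute endpoint and does not reconcile them. The higher one, 75%, supports the power claim and lies above the upper confidence limit of the lower one. The only alteplase figure in the documents close to 75% is the 120-minute rate of 75.1%. The documents do not say that the assumption was taken from there, so that is an observation about the numbers and not a finding about their origin.

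For a fixed absolute margin with equal rates above 50%, a lower rate means a larger binomial variance and less power. Non-inferiority is the second step of the fixed testing sequence. If it fails, the three later tests (superiority to placebo at 60 and at 180 minutes, and superiority to alteplase at 90 minutes) become exploratory. An overstated power at this step therefore understates the planned risk of losing all three.

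**Working it through.** **Inputs.** Arms of 450 and 300, margin 0.10, one-sided 0.025 and equal rates (Protocol 12.1); Wald intervals (Protocol 12.3.5, SAP 9.1); alteplase rates from Protocol Table 9 and SAP Table 3.

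**Formula**, for a common rate p: power = Φ(0.10/SE − 1.96), with SE = √[p(1−p)(1/450 + 1/300)].

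**1. The plan's own figure.** At p = 0.75, SE = √(0.1875 × 0.005556) = 0.03227. Then 0.10/0.03227 = 3.098, and Φ(1.138) = 87.3%. The stated 87% reproduces.

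**2. The plan's 90-minute rate.** The interpolation checks: 516 + (747 − 516) × 60/90 = 670, and 670/995 = 0.6734. Then SE = 0.03496, 0.10/0.03496 = 2.861, and Φ(0.901) = 81.6%. At the CI limits power is 80.0% (64.4%) and 83.6% (70.3%). The exact binomial power of the Wald rule at 67.3% is 81.9%, so the normal approximation is not driving the result.

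**3. Curve shape.** A straight line understates the 90-minute rate if response flattens with time. Two concave curves were fitted to the plan's 30- and 120-minute points. Their forms are assumptions.
- Log-time: 0.5186 + [ln(90/30)/ln(120/30)] × (0.7508 − 0.5186) = 0.7026.
- Exponential saturation from zero, A(1 − e^(−kt)): k = 0.0384 and A = 0.7583 give 0.7344 at 90 minutes.

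**4. Superiority for a 10-point gain**, same 450/300, pooled-variance z test: power = Φ[(0.10 − 1.96·SE₀)/SE₁], where SE₀ uses the pooled rate and SE₁ the separate rates. At 85% v 75%, SE₀ = 0.02924 and SE₁ = 0.03014, giving 92.2% and reproducing the stated 92%.

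| 90-minute alteplase rate | Non-inferiority power | Superiority power (+10 points) |
|---|---|---|
| 75% (assumed in the plan) | 87.3% | 92.2% |
| 73.4% (exponential) | 85.9% | 90.7% |
| 70.3% (log-time) | 83.5% | 87.9% |
| 67.3% (plan's interpolation) | 81.6% | 85.5% |
| 64.4% (lower CI limit) | 80.0% | not computed |

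The overstatement of non-inferiority power is 87.3 − 85.9 = 1.4 points at the least and 87.3 − 80.0 = 7.3 points at the most, or roughly 1 to 7 points.

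**5. Per-Protocol Set.** The planned randomised numbers are 473 and 315. The exclusion rates below are assumed and applied equally to both arms, because the documents give none.

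| Excluded | Power at 67.3% | Power at 73.4% |
|---|---|---|
| 5% | 81.5% | 85.9% |
| 10% | 79.4% | 84.0% |
| 15% | 77.1% | 81.9% |

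At 67.3%, power falls below 80% once exclusions pass about 8.7%.

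**The case against.** **The plan never puts CUSA-081 at 67.3%.** The 67.3% is an alteplase figure, and the reteplase series described in Protocol 1.3 reports 88.5% (123/139) at 60 minutes. The result is sensitive to this: with alteplase at 67.3%, a true CUSA-081 advantage of about 0.76 points restores 87%, and 2 points gives about 93%. That is correct, and it limits the range quoted here to the case of equal rates. But equality is the plan's own assumption for this calculation, and the recalculation keeps it and changes only the level. The sensitivity also runs the other way: a 1-point deficit gives Φ(0.09/0.03506 − 1.96) = 72.8%.

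**The 67.3% is itself soft.** It is interpolated, and its interval treats 670/995 as an observed count, so it makes no allowance for interpolation error. This stands, and it is why the size is given as a range. Both concave curves still fall short of 75%. In the historical data, 75% by 90 minutes would be about 746 of 995, leaving only about one further response before the 747 at 120 minutes.

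**A cautious margin input need not equal an expected rate.** True in principle. But the cautious input to the margin is the lower limit, 64.4%; the 67.3% is the point estimate. If a higher rate is expected in this trial, the documents do not say why.

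**450/300 is a low count for a Day 1 endpoint.** With all 473/315 randomised, power at 67.3% is about 83%. On those numbers 75% gives 88.8%, so a gap of about 5 points remains.

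**The trial has stopped.** SAP 12 says so: "Since the study has been terminated by the Sponsor prematurely for other reasons". The precision obtained now depends on actual enrolment, which the documents do not give. This limits the consequence, but SAP 1.0 still carries the 87% forward.

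**Conclusion.** The concern holds. The 87% is correct arithmetic on an unsourced input that conflicts with the plan's own 90-minute estimate. Under equal rates and 450/300, non-inferiority power at that estimate is about 82%, with a range of 80% to 86% over the published interval and two assumed concave curves. The planned risk of failing the second step is then about 18% instead of 13%, or 14% to 16.5% under the concave curves. Superiority power for a 10-point gain is about 85%, and up to about 91% under a concave curve.

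On 450/300 with equal rates, power stays at 80% or above throughout that range, so the design is not undermined. The missing per-protocol power is a secondary gap, and its size rests entirely on assumed exclusion rates. The point should be corrected as a matter of accurate description; it alters no test or conclusion rule.

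**What to change.** In Protocol 12.1, the Protocol Outline and SAP 5, do one of the following:

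1. Cite the basis for 75% success at 90 minutes in both arms, and say why it differs from the 67.3% used in the margin section.
2. Restate non-inferiority power at 67.3% as about 82%, with a sensitivity range of 80% to 86% for the confidence interval and curve shape under equal rates. Restate power for a 10-point superiority difference as about 85%, up to about 91% if the curve is concave.

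In either case, add non-inferiority power for the Per-Protocol Set, starting from 473/315 under a stated exclusion rate. Because the trial has stopped, the practical place for the correction may be the SAP or the clinical study report.

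The cost is wording and a few recomputed figures, and a slightly less favourable stated power. Sample size, margin, tests and testing order are unchanged.
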